Liposomal Bupivacaine vs Peripheral Nerve Block

Principal Investigator: [name]
[name]
[name]
[contact]

Abstract:

Liposomal bupivacaine has gained interest in recent literature for its potential to be an effective adjunct to other pain control modalities in a multi-modal approach to post-operative pain control. Liposomal bupivacaine is an analgesic that is suspended in lipids to allow for gradual release of the analgesic over a 72-hour period (NAMDARI). From prior literature, the utilization of local analgesics infiltrated into surgical sites have been shown to reduce pain in the immediate post-operative period in foot and ankle surgery (GADEK). However, the evaluation of liposomal bupivacaine in foot and ankle surgery is limited. One prospective study found that the addition to liposomal bupivacaine to a multi-modal pain management protocol for forefoot surgery resulted in decreased pain scores during the first four post-operative days as well as fewer refills of opioid pain medication prescriptions, although both findings were not statically significant (ROBBINS). As the general medical community and public policy makers continue to focus on decreasing the amount of opioid pain medications prescribed and available in the community due to the opioid epidemic, liposomal bupivacaine has the potential to be a useful adjunct in the management of post-operative pain without reliance on opioid prescriptions. The goal of our investigation is to compare the efficacy of local administration of liposomal bupivacaine versus the efficacy of a peripheral nerve block in terms of post-operative pain scores after elective ankle and hindfoot surgery. We hypothesize that there will not be a significant difference in the pain scores of these two groups in opioid naïve patients. Furthermore, we aim to determine if there are differences in the amount of opioid medications utilized for post-operative pain control, patient satisfaction scores, functional outcomes, complications, and unscheduled healthcare contact between the two groups. In order to accomplish our goal and aims, we plan to conduct a randomized, controlled investigation.

Background and Significance:

Liposomal bupivacaine has gained interest in the orthopaedic community for its potential to be a useful adjunct in the control of post-operative pain. Especially with the recent focus on decreasing the number of opioids prescribed and available to the general public due to the opioid epidemic, liposomal bupivacaine is being investigated in numerous orthopaedic sub-specialties as a promising way to control post-operative pain, maintain high patient satisfaction, all the while decreasing dependence on opioids for pain control. The arthroplasty arena has led the way in the investigation of liposomal bupivacaine in the management of post-operative pain. Sabesan, et al. demonstrated excellent pain relief for patients undergoing shoulder arthroplasty who received a local liposomal bupivacaine injection in addition to a single-bolus interscalene block compared to patients who received continuous interscalene nerve block (SABESAN). Yu, et al. demonstrated that patients who received a local liposomal bupivacaine injection after total knee arthroplasty consumed slightly less morphine equivalents of opioids than patients who received a femoral nerve block (YU). Given these findings, the utilization of liposomal bupivacaine in foot and ankle surgery is of interest as well.

From prior literature, the utilization of local analgesics infiltrated into surgical sites have been shown to reduce pain in the immediate post-operative period in foot and ankle surgery (GADEK). However, the evaluation of liposomal bupivacaine in foot and ankle surgery is limited. One prospective study found that the addition to liposomal bupivacaine to a multi-modal pain management protocol for forefoot surgery resulted in decreased pain scores during the first four post-operative days as well as fewer refills of opioid pain medication prescriptions, although both findings were not statically significant (ROBBINS).

The goal of our investigation is to compare the efficacy of local administration of liposomal bupivacaine versus the efficacy of a peripheral nerve block in terms of post-operative pain scores after elective ankle and hindfoot surgery. We hypothesize that there will not be a significant difference in the pain scores of these two groups in opioid naïve patients. Furthermore, we aim to determine if there are differences in the amount of opioid medications utilized for post-operative pain control, patient satisfaction scores, functional outcomes, complications, and unscheduled healthcare contact between the two groups. In order to accomplish our goal and aims, we plan to conduct a randomized, controlled investigation.

Hypothesis and Aims:

Hypothesis:

We hypothesize that there will not be a significant difference in the pain scores of patients randomized into the liposomal bupivacaine group and the peripheral nerve block group in opioid naïve patients.

Specific Aim 1:

To compare post-operative pain scores after elective ankle and hindfoot surgery in patients who receive a local infiltration of liposomal bupivacaine versus a peripheral nerve block.

Specific Aim 2:

To compare opioid consumption in morphine equivalents after elective ankle and hindfoot surgery in the two groups.

Specific Aim 3:

To compare patient satisfaction scores after elective ankle and hindfoot surgery in the two groups.

Specific Aim 4:

To compare functional outcomes after elective ankle and hindfoot surgery in the two groups.

Specific Aim 5:

To compare complication rates after elective ankle and hindfoot surgery in the two groups.

Specific Aim 6:

To compare rates of unscheduled healthcare contact after elective ankle and hindfoot surgery in the two groups.

Study Design:

This is a prospective, randomized trial to investigate whether there is a difference in pain score, opioid consumption, patient satisfaction, functional outcomes, complication rates, and unscheduled healthcare contact associated with local liposomal bupivacaine infiltration versus peripheral nerve block in patient undergoing elective ankle and hindfoot surgery. Approximately 50 patients will be randomized.

Study Population:

Approximate Number of Subjects:

PI: [name]

IRB# 2018-0486

Version 1.1 (07/23/2019)

Approximately 50 total Geisinger patients will participate in the study.

Inclusion Criteria:

1. Patients 18 years of age or older
2. Patients undergoing elective primary ankle or hindfoot surgery (ankle arthrodesis, subtalar arthrodesis, triple arthrodesis, total ankle arthroplasty, peroneal tendon debridement/transfer, Cavus Reconstruction, Medial Displacement Calcaneal Osteotomy, Dwyer Osteotomy)

Exclusion Criteria:

1. Patients who are undergoing revision surgical procedure
2. Patients who have taken opioid pain medications in the past 3 months prior to surgical procedure
3. Patients who have allergies to any of the medications or components of medications investigated in the study
4. Patients currently incarcerated
5. Patients who cannot read and speak English

Study Recruitment:

The study investigators will identify potential study participants in the outpatient clinic. The patients that meet inclusion criteria will be approached by the physician investigator, research coordinator(s), and/or research assistant(s) during their orthopaedic clinic visit and will be asked to participate in the study. After hearing the study explanation, if the patient is interested in participating, the physician investigators, research coordinator(s) and/or research assistant(s) will review, with the patient, the informed consent form asking authorization to access/use their PHI. The patient will sign and date the form after all questions have been satisfactorily answered by the study team. Recruitment materials will consist of the informed consent form.

Study Duration:

Approximate Duration of Subject Participation:

Patients will participate in the study for approximately 3 months – from initial recruitment to end of participation.

Approximate Duration of Study:

The study will be completed in approximately 12 months. The end of the study is the last visit of the last subject, or end of collection of data from the patient's electronic health record.

Procedures:

Patients who meet inclusion criteria will undergo a selection process, and if they choose to participate will be randomized into one of two groups. The randomization scheme will be created with the use of an internet based randomization website (<https://www.randomizer.org>). Qualifying subjects will be randomized into one of two groups prior to their surgery:

PI: [name]

IRB# 2018-0486

Version 1.1 (07/23/2019)

1. Liposomal Bupivacaine Group**a. Pre-operative**

i. No peripheral nerve block will be given

b. Intraoperative

i. Local infiltration of 20cc of Liposomal Bupivacaine infiltrated to the surgical area

c. Post-operative (At Discharge)

i. Oxycodone 5mg every 6 hours as needed for pain (30 tablets)

ii. Acetaminophen 500mg every 6 hours scheduled

2. Peripheral Nerve Block Group**a. Preoperative**

i. Peripheral Nerve Block performed by anesthesia team (blocks will be given by same anesthesia provider utilizing same technique every time in order to reduce variations in delivery of peripheral nerve block).

b. Intraoperative

i. No local analgesic agent infiltration

c. Post-operative (At Discharge)

i. Oxycodone 5mg every 6 hours as needed for pain (30 tablets)

ii. Acetaminophen 500mg every 6 hours scheduled

Patients will be randomized as to which analgesia regimen they will receive. The surgeon will not be blinded.

On the day that the patient is consented for the study, they will complete the following standard of care assessments in clinic:

1. VAS Pain Scale
2. Pain Catastrophizing Scale
3. PROMIS Self-Efficacy of Managing Symptoms

On the day of surgery, all qualifying patients will undergo their elective ankle or hindfoot surgery under standard practices. Randomized patients will receive pre-operative peripheral nerve block prior to the procedure. The participating surgeon will perform the procedure in accordance with their standard practice. Liposomal Bupivacaine will be injected prior to incision and after wound closure. Patients will

PI: [name]

IRB# 2018-0486

Version 1.1 (07/23/2019)

be placed in sterile dressings and a post-operative splint in accordance with the surgeon's standard practice. All patients will receive discharge instructions based on the surgeon's standard practice. All patients will receive the same post-operative opioid pain regimen.

Patients will keep a pain journal, documenting their pain from postoperative days 1-7. It will include pain score as well as pain medication utilization documentation starting from immediately in the Post-Anesthesia Care Unit, 6 hours post-op, and 12 hours post-op. Afterwards, participants will be asked to document pain score and pain medication utilization daily from post-operative days 1-7. They will bring their pain journal with them to their first postoperative visit.

Patients will be seen at 2 weeks and 6 weeks postoperatively. During these visits, a routine wound check will be performed. The patient's range of motion and pain will be assessed. Any complications will be recorded. All postoperative care other than the medications prescribed at the time of discharge will be in accordance with each surgeon's standard practice. At each of these two visits, patients will complete the following assessments:

1. VAS Pain Scale
2. Pain Medication Utilization Questionnaire
3. Pain journal collection

At the conclusion of the 6-week post-operative period, the EMR will be reviewed and any instances of unscheduled healthcare contact (email, MyGeisinger messages, telephone calls, unscheduled clinic visits, ED visits) will be recorded and analyzed for cause.

All surgeons participating in the study will adhere to the randomization, treatment and follow-up protocol. There will be 2 participating sites within the Geisinger system (GMC and GMC Woodbine) whom will participate in this research project.

Study Time and Events Table

| Study Procedures | Visit ~pre-surgery | Visit Day of Surgery | 0, 6, & 12 Hours Post Op | Visit 2 week follow-up | Visit 6 week Follow-up |
|---|--------------------|----------------------|--------------------------|------------------------|------------------------|
| Office Visit | X | | | X | X |
| Prescreen | X | | | | |
| Provide Info Sheet | X | | | | |
| Review Inclusion/Exclusion | X | X | | | |
| Demographics, medical history, habits, historical diagnoses | X | | | | |
| Consent of Patient | X | | | | |
| Randomization | X | | | | |
| Outcome measures / examination assessment recorded | X | | X | X | X |
| Analgesia administration | | X | | | |
| Surgery | | X | | | |
| AE / Complication Reporting | | X | X | X | X |

Primary Endpoints:

The primary endpoint is to determine if there is a statistically significant difference in pain scores (VAS Pain Scale) for patients undergoing elective ankle and hindfoot surgery randomized to a group receiving intra-operative liposomal bupivacaine infiltration versus a group receiving a peripheral nerve block.

Secondary Endpoints:

1. Differences in morphine equivalents consumed for post-operative pain control
2. Difference in patient satisfaction score
3. Differences in functional outcomes
4. Difference in complications
5. Differences in unscheduled healthcare contact

Statistics:

PI: [name]

IRB# 2018-0486

Version 1.1 (07/23/2019)

Statistical analysis will be performed by [name]

Data Management

Data to be Collected:

The following data will be collected from the EMR:

- PHI elements (will not be included in final dataset)
- Medical Record Number (MRN)
- Name
- Date of Birth
- Patient Demographics (Age, gender, weight, height, Body Mass Index (BMI))
- Medical History
- Narcotic use history
- Inflammatory or Rheumatoid Arthritis
- Complications / AE
- Wound Hematoma
- Superficial wound infection (defined as any prescription for post-op antibiotics)
- Wound complications
- Deep infection (defined as need for surgical irrigation and debridement)
- Crossover
- Number of patients randomized to liposomal bupivacaine group that request peripheral nerve block
- Unscheduled healthcare contact and reason for contact
- Phone calls
- Emails
- MyGeisinger Messages
- Unscheduled clinic visits
- ED visits
- Dates
- Date(s) and information related to admission, surgery, and discharge
- Date(s) and information related to clinic visits

The following data will be collected during the patient clinic visits:

- VAS Pain Scale (0-10)
- Pain journal from post-operative days 0-7 including pain medication utilization and pain scores

Data Collection and Storage

The data points outlined above will be reviewed and collected from the EMR by the study coordinator(s), project coordinator(s) and/or co-investigators. A data request will be submitted to the BC Data Broker, an independent person from the study team.

A member of the IRB-approved Geisinger study team will perform a manual chart review for data points not captured during the BC data pull. A member of the IRB approved study team will randomly assign

PI: [name]

IRB# 2018-0486

Version 1.1 (07/23/2019)

study ID numbers in order to protect the identity of the subject. After the dataset has been de-identified, an IRB-approved study team member will forward the completed dataset to [name] for analysis. All study data will be kept in GHS maintained username/password-protected computer files and hard copy data will be double locked and accessible only to the study investigators in the locked office of the Study Coordinator. Only group-level information without personal identifiers will be included when presenting results or submitting manuscripts for publication.

Personal or sensitive information that could be potentially damaging to participants (e.g. relating to illegal behaviors, alcohol or drug use, sexual attitudes, mental health, etc.) will not be collected. With concerns to HIV/AIDS status, if the status is already in the participant's medical record it will be reported into the CRF as a "yes" or "no," otherwise it will be reported in the CRF as "not assessed." Regarding collected mental health information that could be potentially damaging to participants, participants indicating that they are very depressed, thus raising concern regarding their mental state, will be referred to their primary care physician.

No PHI will be shared outside of the IRB approved study staff.

Records Retention

Records of data generated in the course of the study will be kept indefinitely and may be used for future research purposes.

Adverse Event Reporting

Clinical adverse events (AEs) will be monitored throughout the study. All AEs will be reported to the institutional review board (IRB) according to IRB policy. The date and time of onset and outcome, course, intensity, action taken, and causality to study treatment will be assessed by the study PI.

Definitions

An adverse event (AE) is any untoward, undesired, or unplanned event in the form of signs, symptoms, disease, or laboratory or physiologic observations occurring in a person given a test article or in a clinical study. The event does not need to be causally related to the test article or clinical study.

Adverse Events related to Elective Ankle and Hindfoot Surgery:

- Infection
- Wound healing issues
- Persistent pain
- Peripheral nerve injury
- Arterial injury
- Wound complications

A protocol-related adverse event is an AE occurring during a clinical study that is not related to the test article, but is considered by the investigator or the medical monitor (or designee) to be related to the research conditions, i.e., related to the fact that a subject is participating in the study. For example, a

protocol-related AE may be an untoward event occurring during a washout period or an event related to a medical procedure required by the protocol.

Recording and Reporting

A subject's AEs will be recorded and reported from the signing of the informed consent form to end of study period.

Protection of human subjects

Informed Consent

The investigator will provide for the protection of the subjects by following all applicable regulations. The informed consent form will be submitted to the IRB for review and approval. Prior to having any study procedures performed, the patient will be asked to read and then sign the informed consent form if they agree to participate in the study. The subject will receive a copy of the signed/dated informed consent form for their records. The original copy of the informed consent form will be scanned into the subject's EMR and the hardcopy will be filed in the subject's study binder. The rights and welfare of the subjects will not be affected. We are requesting to observe and record variables that are normally collected and entered into the patient's EMR in the course of standard clinical care. The purpose of recording data for this prospective study (in addition to the EMR) is simply to ensure that discrete, standardized format (since some variables, while stored in the EMR, may appear in physician notes as free text).

There is very little to no risk associated with this study. The risk to study participants is related to accidental disclosure of PHI (i.e. MRNs, dates). Any time information is collected for a study there is a small risk of breach confidentiality. However, this risk is not greater than the risk that already exists in clinical settings when handling medical data.

A partial waiver of HIPAA authorization is being requested for this study. A waiver is necessary for the research to be practically conducted because the research team must review the patient's PHI to determine eligibility. The research team would be unaware of potential eligible patients without reviewing that patient's relevant medical information. If the patient does not meet eligibility criteria, they will not be approached to partake in the study. While PHI is being requested, it is the minimal amount necessary to ensure patients are eligible based on the inclusion criteria.

Protection of Human Subjects Against Risks

The investigator will provide for the protection of the subjects by following all applicable regulations. Anticipated risks in this study are minimal. This study will not affect patient care or access to care. The major risk to human subjects in this study is the accidental disclosure of PHI. In this regard, the assignment of a coded test ID number to each individual participant and the protocol of providing only the necessary associated clinical information to the remainder of the research team mitigate this risk.

All study data will be kept in Geisinger Health System maintained username/password-protected computer files and hard copy data will be double locked and accessible only to the study investigators. Only group-level information without personal identifiers will be included when presenting results or submitting manuscripts for publication.

Publication Plan:

We plan to prepare and submit the results of this study for presentation at national meetings and in peer-reviewed journals.

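### The only hypothesis predicts a non-significant difference test and no margin is given, so a result that fulfils it would not show similar pain control

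*Protocol*

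**What the plan says.** The hypothesis stands in three places in the protocol. The Abstract, and the goal paragraph that closes Background and Significance, both say "We hypothesize that there will not be a significant difference in the pain scores of these two groups" in patients who have not been taking opioids. Under Hypothesis and Aims it is repeated as "We hypothesize that there will not be a significant difference in the pain scores of patients randomized into the liposomal bupivacaine group" and the nerve block group. No other hypothesis is stated.

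The rest of the protocol asks a difference question:

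- Specific Aim 1: "To compare post-operative pain scores after elective ankle and hindfoot surgery in patients who receive a local infiltration of liposomal bupivacaine" or a nerve block.
- Study Design: "This is a prospective, randomized trial to investigate whether there is a difference in pain score" and in the secondary outcomes.
- Primary Endpoints: "The primary endpoint is to determine if there is a statistically significant difference in pain scores (VAS Pain Scale"), liposomal bupivacaine against block.

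About 50 patients are to be randomised. The protocol contains no equivalence or non-inferiority wording about the two arms, no tolerated difference and no CI criterion. The Statistics section says only who will do the analysis.

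**The concern.** The hypothesis forecasts how a test will come out. It does not say how close the two regimens must be. A difference test can give evidence that the arms differ. When it fails to reject, the cause may be that the arms are close or that the trial was too imprecise to tell, and the p-value does not separate the two.

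Both cases fulfil the hypothesis as written. The forecast is thus easiest to meet when the trial is least informative. The comparison is between two active regimens, so a report that the hypothesis was confirmed could easily be taken to mean that infiltration does as well as a block. The interval might at the same time include a disadvantage that patients would notice.

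**Working it through.** **Logic.** Set the two statements side by side. The hypothesis is fulfilled if the primary test gives p > 0.05 and contradicted if p < 0.05. Similar pain control would need the CI for the difference to exclude every difference that matters, and the protocol names no such difference. Fulfilling the hypothesis and showing similarity are therefore separate events, whatever the SD.

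**Inputs.** From the protocol: about 50 patients, two groups, VAS scored 0-10. Assumed, because not stated: 25 per arm, two-sided 0.05, one unadjusted reading, SD 1.5 to 3.0 points. The figure of 50 cannot be reproduced, since no effect size, SD, power or margin is given. The 1.5-point difference is an example, not a proposed threshold.

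**Precision.** SE = SD × √(2/25). The 95% CI half-width is t(0.975, 48 df) × SE, with t = 2.011. For SD 2.0: SE = 2.0 × 0.2828 = 0.566, and 2.011 × 0.566 = 1.14.

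**Chance of a non-significant result.** This is P(|T| < 2.011), with T non-central t on 48 df and non-centrality (true difference)/SE. For a 1.5-point difference and SD 2.0 the non-centrality is 1.5/0.566 = 2.65, which gives 0.262.

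| | SD 1.5 | SD 2.0 | SD 2.5 | SD 3.0 |
|---|---|---|---|---|
| SE | 0.424 | 0.566 | 0.707 | 0.849 |
| 95% CI half-width | 0.85 | 1.14 | 1.42 | 1.71 |
| Non-significant, true difference 1.0 | 36% | 59% | 72% | 79% |
| Non-significant, true difference 1.5 | 7% | 26% | 45% | 59% |
| Non-significant, true difference 2.0 | 0.4% | 7% | 21% | 36% |

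**Averaging readings.** The SD of a mean of k readings with within-patient correlation r is SD × √((1 + (k − 1)r)/k). With r = 0.5 assumed, the factor is 0.816 for k = 3 and 0.764 for k = 6. A true 1.5-point difference is then non-significant in 1% / 11% / 28% / 44% of trials (k = 3) and 0.5% / 7.5% / 22% / 38% (k = 6).

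**Effect of trial size.** With a true difference of 1 point and SD 2.5, the same formula with 2n − 2 df gives a non-significant result with probability 0.492 at 50 per arm, 0.717 at 25 and 0.865 at 10. The smaller the trial, the more often the hypothesis is met although the arms differ.

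**The case against.** The best defence is that the aims, the design statement and the primary endpoint all ask an ordinary two-sided difference question. Such a trial needs no margin, and expecting a null result does not make the test invalid. Rules of interpretation and CI reporting may also sit in a statistical analysis plan that is not shown. Much of this stands: the difference test is legitimate, and the absence of alpha, power or an analysis method from the protocol is no fault. It does not remove the mismatch, because the hypothesis and the endpoint are both fixed in the protocol, and the hypothesis sentence would still need changing.

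Four stronger readings are tempting and are not supported.

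- A reader might infer that the planned test can never support the hypothesis. As worded, the hypothesis predicts a non-significant result, and a non-significant result does meet it. The trouble is that meeting it says little. For the same reason, the 95% chance of non-significance applies only if the true means are exactly equal, not whenever the stated prediction is right.
- A reader might infer that the investigators will report p > 0.05 as similarity. The protocol states no decision rule and makes no claim that the arms are comparable.
- A reader might look for a clue in the cited forefoot study, summarised as having "resulted in decreased pain scores during the first four post-operative days", with the caveat "although both findings were not statically significant". That is background on another study and says nothing about how this trial will read its own result.
- A reader might infer that 50 patients are too few. Without an SD, a relevant difference or a margin, the documents cannot show this.

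**Conclusion.** The point holds in a limited form. The hypothesis predicts a non-significant result from the primary difference test, no margin is given, and a result that fulfils it would not show similar pain control. This follows from the protocol's own wording and needs no assumed figure.

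The practical size does depend on assumptions. For a true 1.5-point difference at 25 per arm, the chance of a non-significant result runs from 7% (SD 1.5) to 59% (SD 3.0) for one reading, and from 0.5% to 38% for a mean of six readings with correlation 0.5. The risk is small if the SD is low and scores are averaged, and large otherwise.

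This should be fixed before results are seen. It is a fault of wording and interpretation on the primary question; it does not make the planned test or the sample size wrong.

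**What to change.** Replace the hypothesis sentence in the Abstract, in the goal paragraph of Background and Significance, and under Hypothesis with a difference question that matches Specific Aim 1. For example: *We will compare pain scores between the groups and report the difference (liposomal bupivacaine minus block) with its two-sided 95% CI; a p-value above 0.05 alone is inconclusive and will not be reported as similarity.* Keep the difference test under Primary Endpoints and add the same interpretation sentence there.

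Only if the sponsor wants to claim comparability: pre-specify a justified margin and a CI rule before results are seen, and state the power that about 50 patients give. For non-inferiority, the upper 95% limit must lie below the margin. For equivalence, both limits of the 90% CI, or of the stricter 95% CI if chosen, must lie inside it.

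**Cost.** A few sentences and no patients. Some results that would have been called no difference become inconclusive. The optional claim may need more patients. At 25 per arm, one reading, arms truly equal and SD 1.5 / 2.0 / 2.5 / 3.0, with an illustrative 1.5-point margin, power is:

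- non-inferiority: 93% / 74% / 55% / 41%
- equivalence by 90% CI: 93% / 67% / 35% / 10%
- equivalence by 95% CI: 87% / 48% / 12% / 1%

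### The surgery-day text gives a nerve block to randomized patients without naming an arm, against the liposomal-arm rule; separately, the one crossover measure described counts block requests in one arm, not treatment received

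*Protocol*

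**What the plan says.** **Who is randomized.** Protocol, Procedures: "Qualifying subjects will be randomized into one of two groups prior to their surgery". No participant is followed outside the two groups.

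**Arm lists (Procedures).** For the Liposomal Bupivacaine Group, the pre-operative entry is "No peripheral nerve block will be given" and the intraoperative entry is "Local infiltration of 20cc of Liposomal Bupivacaine infiltrated to the surgical area". For the Peripheral Nerve Block Group, the anesthesia team performs a block before surgery, and the intraoperative entry is "No local analgesic agent infiltration".

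**Day of surgery (Procedures, narrative after the arm lists).** Two sentences deal with analgesia: "Randomized patients will receive pre-operative peripheral nerve block prior to the procedure", and shortly afterwards "Liposomal Bupivacaine will be injected prior to incision and after wound closure". Neither names an arm.

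**Purpose.** Specific Aim 1 compares pain scores "in patients who receive a local infiltration of liposomal bupivacaine versus a peripheral nerve block", and the primary endpoint sets the same two groups against each other. The Hypothesis reads in part: "We hypothesize that there will not be a significant difference in the pain scores of patients randomized into the liposomal bupivacaine group".

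**Crossover (Data Management, Data to be Collected).** The word Crossover is followed by one related item: how many patients randomized to the liposomal bupivacaine group ask for a peripheral nerve block. The list also covers information related to surgery in general terms. Data Collection and Storage plans a manual chart review for data points that the electronic pull misses.

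**The concern.** Block versus infiltration is the only planned difference between the groups. A narrative sentence that assigns the block without naming an arm conflicts with the arm list on exactly that difference. Two sites take part, and the adherence statement in Procedures asks surgeons to follow the randomization and treatment protocol. Text that staff are asked to follow should not give two answers to who receives a block.

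The crossover item raises a related question after the fact. The trial expects no significant difference. If that is what it finds, a reader will ask whether the groups were in fact treated differently, because patients who receive the other group's treatment make the groups more alike in what they received. A count of requests in one group does not answer that.

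**Working it through.** The documents give no figure to reproduce on this point. The first three steps compare text; the fourth is simple arithmetic.

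**Step 1. Does the block sentence conflict with an arm rule?**

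| Place in Procedures | Liposomal group | Block group |
|---|---|---|
| Arm lists, pre-operative | No block | Block |
| Surgery-day block sentence, read literally | Block (all are randomized) | Block |

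The rows disagree for the liposomal group and agree for the block group. Of the two surgery-day analgesia sentences, one (the block sentence) therefore conflicts directly with an arm rule: 1 of 2.

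**Step 2. What would the literal reading do to the comparison?** Change only the block sentence, and leave the liposomal bupivacaine sentence with the arm to which that drug belongs.

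- Liposomal group: infiltration alone becomes block plus infiltration.
- Block group: block alone, unchanged.
- Comparison: infiltration versus block becomes block plus infiltration versus block.

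The groups still differ, but the trial would be answering a different question from the one in Specific Aim 1.

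**Step 3. What does the crossover item capture?** Take Crossover as the heading of the item that follows it. Each kind of departure from assignment can then be set against that item.

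| Situation | Shown by the item? |
|---|---|
| Liposomal group, block requested and given | Request counted; receipt not recorded |
| Liposomal group, block requested and not given | Request counted; non-receipt not recorded |
| Liposomal group, block given without a request | Not counted |
| Block group, block not given | No named item |
| Block group, infiltration given | No named item |

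The item covers 1 of 2 arms. Within that arm, request and receipt can differ in two ways (second and third rows). The Study Time and Events Table lists analgesia administration as a day-of-surgery procedure, not as a data item, and the general surgery-information item does not name analgesia.

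**Step 4. Burden of recording receipt.** Study Design gives about 50 randomized patients. Two yes/no fields × 50 patients = 100 entries, approximately.

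The documents give no crossover rate, so the effect of any departures on the pain comparison cannot be calculated. The counts above describe the wording and do not measure harm.

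**The case against.** **The intent is plain.** The arm lists state block or no block by group, Procedures says that randomization decides the regimen, and Specific Aim 1 and the primary endpoint agree. An item counting block requests in the liposomal group would make little sense if all of those patients received a block. The sentence can also be taken as shorthand for patients randomized to the block. All of this stands, and it makes the sentence a drafting error and not a flaw of design. It does not make the sentence consistent with the arm list.

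**The contrast would vanish.** A reader might infer that following the surgery-day text literally would treat both groups identically. That requires the liposomal bupivacaine sentence to cover both groups too. It names no patients at all and reads naturally as describing the drug of one arm, so the documents do not support the inference. Nor is its timing a second contradiction: how the two injection points relate to the volume in the arm list is not spelled out, but the two statements are compatible.

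**The crossover point is a preference about data collection.** Several parts of this objection stand. The list was read here without its indentation, so Crossover may be an item in its own right, not limited to one arm. No aim or endpoint uses the count. Nothing in the Protocol defines crossover as a request or uses requests to classify patients, so a reader who infers that the item misclassifies patients goes too far. The facts are probably in the chart, and deviation handling may be set out in an analysis plan that is not shown. What remains is narrower: the one crossover measure that the Protocol describes directs the extractor to requests in one group. The analyst receives a finished, de-identified dataset, so treatment received will be available only if someone has extracted it.

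**Conclusion.** Both parts hold in limited form.

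The first is certain from the text. One surgery-day sentence, read literally, contradicts the pre-operative rule of one arm. Because the intent can be recovered elsewhere in the Protocol, it is a drafting error in operative text, worth correcting because it concerns the trial's only planned contrast.

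The second is a cheap improvement and rests on reading Crossover as a heading. On that reading, the only crossover measure described covers requests in 1 of 2 arms and leaves treatment received without a named item. A reader might infer that the comparison by randomized group is thereby invalid or biased. The documents do not support that: the comparison does not use the item. It is the interpretation of a no-difference result that needs treatment received by arm.

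**What to change.** 1. Reconcile the arm lists and the surgery-day paragraph in Procedures so that each surgery-day analgesia sentence names the arm to which it applies. The investigators decide the content. The cost is a wording change in two sentences.

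2. Under Data to be Collected, add two items for every randomized patient in both groups: peripheral nerve block received (yes/no) and local infiltration received (yes/no). Take them from the electronic pull or the manual chart review already planned. Keep patient requests for a block as a separate item. The cost is the roughly 100 extra entries worked out above.
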